6.2. Serious Adverse Events (SAE) Reporting

Study site personnel will immediately alert the site PI as well as the coordinating center PI of any serious adverse event (defined below) experienced by a subject that is related to the study or results in death. In addition, serious

adverse events related to study must be reported to regulatory authorities according to the definitions and timelines specified in the local laws and regulations.

A Serious Adverse Event is any untoward medical occurrence that:

- Results in death
- Is life-threatening (defined as an event in which the patient was at risk of death at the time of the event; it does not refer to an event which hypothetically might have caused death if it were more severe;
- Requires inpatient hospitalization or causes prolongation of existing hospitalization;
- Results in significant or persistent disability or incapacity (defined as a short or long term, temporary, chronic or permanent disruption of the patient's ability to carry out normal life functions)
- Is a congenital anomaly or birth defect
- Results in the development of drug dependency or drug abuse or
- Is an important medical event (defined as a medical event that may not be immediately life-threatening or result in death or hospitalization but, based upon appropriate medical and scientific judgment, may jeopardize the patient or may require intervention (e.g., medical or surgical) to prevent one of the other serious outcomes listed in the above definition). Examples of such events include, but are not limited to intensive treatment in an emergency room or at home for allergic bronchospasm; blood dyscrasias or convulsions that do not result in hospitalization).

Non-Serious Adverse Events – all other events that do not meet the SAE criteria.

7. Data Reporting/Regulatory Considerations

7.1. Data Entry

The research coordinators, data manager and PI are responsible for ensuring that data abstraction (information required by the protocol) is completed in a timely manner for every subject enrolled on study. De-identified

subjects' data will be entered by the site CRC into a secure electronic database (REDCap) by CGSU data managers. REDCap is a secure and HIPAA compliant web-based application .The data are backed up daily and stored on a secure server managed by Duke University School of Medicine IT Department. The PI, study coordinators and the CGSU data management staff are the only key personnel who will have access to the password-protected database. Subjects' surveys will also be administered through REDCap. Subjects will be assigned access to the system upon study registration and will be provided with the necessary directions by the study coordinators. The CGSU data management staff and PI will systematically review the information entered into the database. Errors or omissions will be documented and maintained with the study files. When the database has been declared complete and accurate, the database will be locked.

7.2. Data Storage and Confidentiality

Subject confidentiality will be ensured at all times. Each subject will be assigned a unique study ID. Only key research personnel will have access to the list of study IDs and patient names for the purposes of scheduling follow-up surveys and obtaining laboratory test results. Subject identifiers will not be made available to any other institutions, hospitals, insurers, or agencies. The results of studies emerging from this work may be published but individual subjects will not be identifiable in these publications.

It is the PI's responsibility to ensure the subjects' privacy. However, in compliance with federal guidelines, the investigator will permit a representative from the coordinating center, Duke Clinical Genomics Study Unit (CGSU)-Center for Applied Genomics and Precision Medicine (CAGPM) , to review that portion of the subject's medical record that is directly related to the study. This will include all relevant study documentation including medical histories to verify eligibility and laboratory test results to verify transcription accuracy. As part of the required content of informed consent, the subject will be informed that his/her medical record, may be reviewed.

7.3. Records Retention

The Investigator must retain source documents, and case histories designed to record all observations and other data pertinent to the investigation (e.g. case report form) for the maximum period required by applicable regulations and guidelines, or Institution procedures.

If a change in the PI occurs, the records shall be transferred to a mutually agreed upon designee (e.g., another Investigator, IRB).

8. Statistical Considerations

8.1. Sample Size/Power Calculation

The objective of the power analysis was to determine the minimum sample size needed to reject the null hypothesis that the three-way genetic information by health coaching by time interaction was equal to zero in the context of a longitudinal general linear mixed model. The model was assumed to have two levels of genetic information (present or absent), two levels of health coaching (present or absent), and five levels of time (0, 1.5, 3, 6 and 12 months after randomization). In producing the required sample-size estimates, we further assumed that each of the four group means over time would take on standardized mean values. The type I error rate was set to be no greater than .025 as there will be two primary analyses. Controlling each one at no greater than .025 controls the overall experiment type I error rate to be no greater than .05. Calculations indicated that with a sample size of 99 subjects per group, or 396 total, the power to reject the null hypothesis concerning the three-way interaction was .80. Assuming an attrition rate of at most 15% and the current pilot diabetes study attrition of 11%, over the 12 month time period we calculated a possible required sample size of $(396/.86)=460$ to attain the target sample of 400. Sample size calculations are not provided for detecting the direct effects or interactive effects of the two interventions pooled over time, primarily because we expect the genetic information by health coaching interaction to change over time, as reflected in the three-way interaction.

Due to delayed/slow recruitment the sample size is revised as following (modification approved in contract amendment):

A reduced sample size, but collecting data out to 12 months as planned:

- a. Coming from the stance that we want to preserve as much of the original thinking behind the power analysis as possible, we eliminated the calculation and testing of the three way

interaction which was originally planned. This three way interaction said that the interaction of Health Coaching and genetic testing peaks at 6 months. The idea was that there was a synergy between genetic testing and health coaching which would push health behavior means for the subjects receiving both components to far greater than the individual effects of either one. Elimination of the three way interaction takes away our ability to say when this occurs (time).

Pattern	Type I error rate	Power	Within Person Correlation	Sample Size per Group	Total Sample Size
1	.025	.80	.350	25	100
1	.025	.85	.350	27	108
2	.025	.80	.350	44	176
2	.025	.85	.350	49	196
3	.025	.80	.350	56	224
3	.025	.85	.350	63	252

- b. Means for the four groups pooled across time showing JUST the coaching by genetics testing interaction for each pattern.
- c. Examining the health coaching by time and the genetic testing by time interactions. Assuming the same means over time for pattern 2, the means for the two interactions would be as shown in the two tables immediately below.

Health coaching by time interaction for pattern 2

	NO HC	HC
0	0.05	0.05
1.2	0.15	0.5
3	0.275	0.95
6	0.125	1.5
12	0.05	0.85

Genetic testing by time interaction for pattern 2

	No Genetics	Genetics
0	0.05	0.05
1.2	0.225	0.425
3	0.425	0.8

6	0.525	1.1
12	0.225	0.675

d. Results of power calculations when the three way interaction for the groups, as well as the three way interaction for time by health coaching by genetic testing are eliminated. These are the power for detecting the interaction which is the smallest (the genetic testing one).

Pattern	Type I error rate	Power	Within Person Correlation	Sample Size per Group	Total Sample Size
2	.025	.80	.350	43	172
2	.025	.85	.350	49	196

While we will have lost the power to examine a 3-way interaction (health coaching by genetic risk testing by time), with the participants, we will still be able to:

- 1) Examine 2 way interaction effects of health coaching by time and genetic risk testing by time (estimated minimum sample needed 172-196);
AND/OR
- 2) Examine the 2 way interaction of health coaching and genetic risk testing (comparative effectiveness without time point considered in interaction; estimated sample needed 176-196).

Assuming an attrition rate of at most 15% the required minimum sample size is 212.

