8.2. Analysis Plan

Demographic characteristics of the sample (income level, age, gender, race/ethnicity, educational level) will be provided using descriptive statistics to describe the overall sample and by group to ensure that randomization was effective. Distribution of variables will be determined prior to further statistical analysis. SAS software (80) will be used for all analyses.

To address the primary aims, mixed models will be used. The first aim is to determine the direct and interactive effects of genetic risk information incorporated with standard CHD/T2D risk counseling and a health coaching intervention for CHD/T2D on behavior change (diet, physical activity) in AF primary care patients over 12 months. The goals of the statistical analysis will be to quantify: (1) the extent to which genetic risk counseling influences the trajectory of change in physical activity and diet measures from baseline to 3, 6, and 12 months; and (2) the extent to which the genetic risk information augments the trajectory of the effects of health coaching on diet and physical activity measures over the same time period. We will fit two general linear mixed models to these data (81), with

physical activity and diet measures at each of the five points in time. For either model, there will be three independent variables: genetic risk information (G) with values of 1 or 0, health coaching (HC), also with values of 1 or 0, and time since randomization, with values of 0, 3, 6, and 12 months. Within the context of the linear mixed model, we should observe a statistically significant three way interaction of time by genetic information by health coaching. The particular type of longitudinal model selected for analysis will depend upon preliminary analyses of the data. For example, a subject specific (also called hierarchical) model with random intercept and slope assumes that within subject variances increase or decrease over time. A model hypothesizing only a random intercept does not assume that within subject variances show this pattern. Another consideration will be the extent of missing data; some longitudinal models are better than others at handling missing data.

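### Section 8.1's overall type I error of .05 is not supported for the revised plan: the two tests are never named, and the primary analysis can hold more than two

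*Combined protocol and SAP*

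**What the plan says.** Section 8.1 explains its significance level as follows: "The type I error rate was set to be no greater than .025 as there will be two primary analyses". It then states that "Controlling each one at no greater than .025 controls the overall experiment type I error rate to be no greater than .05". The test sized in that paragraph is the three-way interaction of genetic information (G), health coaching (HC) and time. The two analyses are not identified.

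After slow recruitment, the same section says "we eliminated the calculation and testing of the three way" interaction. In its place it says the reduced sample can serve two purposes, joined by and/or:

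- "Examine 2 way interaction effects of health coaching by time and genetic risk testing by time"
- "Examine the 2 way interaction of health coaching and genetic risk testing"

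Both revised power tables keep .025. The count of analyses is not restated and no option is chosen.

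Other sections bear on the count:

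- **Section 8.2, behavioral outcomes:** "We will fit two general linear mixed models to these data", for physical activity and diet. It adds that "we should observe a statistically significant three way interaction of time by genetic information by health coaching".
- **Section 8.2, metabolic outcomes:** fasting glucose, SBP, BMI, waist circumference, LDL, triglycerides and total cholesterol form the second half of the primary analysis, with the same models.
- **Section 5** describes the primary outcomes as behavioral.
- **Section 2 and Table 2** make clinical outcomes primary too. The primary aims in section 2 also cover main effects, smoking, Air Force fitness score, Framingham score and diabetes risk score.

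Apart from the .025 sentence, no multiplicity rule is given.

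**The concern.** An error rate of .05 means something only if the set of tests it covers is fixed. The sentence may have fitted the original plan: one three-way test in the diet model and one in the activity model makes two. The revision removed that test and left a choice among one, two or three interactions per outcome. Separately, the sections disagree on whether the metabolic outcomes belong to the primary set.

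Readers of the report will take .05 as the error rate of the primary analysis. As written, the interaction and the outcomes could be selected after results are seen and still be reported under that figure. An analyst who follows section 8.2 literally would run more than two primary tests at .025.

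**Working it through.** **Inputs.** Per-test level .025, claimed overall rate .05, the three candidate interactions and the required totals: section 8.1. Two behavioral and seven metabolic outcomes: section 8.2. Enrollment of 250: section 5.1. Attrition of 15%: section 8.1.

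**Step 1. The plan's own figure.** The Bonferroni bound for two tests is 2 × .025 = .05, as stated. If the tests are independent, 1 − .975² = .049. The arithmetic is correct for two tests.

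**Step 2. Other counts the text allows.** For k tests at .025, the bound is k × .025 and the independent value is 1 − .975^k. Outcomes measured on the same participants are likely to be correlated, so I also simulated 400,000 draws of two-sided z tests. I assumed that all nulls are true, that outcomes share a common correlation r, and that interactions within an outcome are independent. The documents give no outcome correlations, so r is shown as a range.

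| Tests counted | k | Bound | r = 0 | r = .5 | r = .9 |
|---|---|---|---|---|---|
| 2 outcomes × 1 interaction | 2 | .050 | .049 | .047 | .036 |
| Diet, activity × HC×time, G×time | 4 | .100 | .096 | .091 | .071 |
| Diet, activity × all three | 6 | .150 | .141 | .132 | .104 |
| All 9 outcomes × 1 | 9 | .225 | .204 | .151 | .067 |
| All 9 outcomes × all three | 27 | .675 | .495 | .388 | .189 |

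The r = 0 column is an upper limit under these assumptions, since pairs such as BMI and waist, or total cholesterol and LDL, are likely correlated. The three-way test is not counted, because section 8.1 removed it. Replacing the z tests by chi-square tests (3 df for each time interaction, 1 df for HC×G) changes the rows with time interactions little: at r = .5, .092 for four tests, .133 for six and .397 for 27.

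**Step 3. Power if the tests are restricted or adjusted.** Planned completers are 250 × .85 = 212.5, taken as 212. I set the noncentrality λ to give .80 power at .025 at section 8.1's required total (9.505 for 1 df, 12.908 for 3 df), then multiplied it by 212 over that total.

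- HC×G, pattern 2 (required 176): 9.505 × 212/176 = 11.449, power .873.
- HC×G, pattern 1 (required 100): .988. Pattern 3 (required 224): .776.
- G×time, pattern 2 (required 172): 12.908 × 212/172 = 15.910, power .889. With 4 df it is .891.
- Four tests, first Holm step .05/4 = .0125: G×time about .84.
- Six tests, first Holm step .05/6 = .0083: G×time about .80, HC×G under pattern 2 about .77.

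**Step 4. How firm that power is.** If only section 8.1's minimum of 212 enroll, about 180 complete (212 × .85 = 180.2). The same scaling then gives G×time .82, .75 and .70 at .025, .0125 and .0083, and HC×G under pattern 2 .81, .73 and .68. Scaling also takes section 8.1's .80 as given. Computing G×time directly from the printed pattern 2 means (assuming SD 1, compound symmetry and correlation .35) gives .77 at 43 per group against the stated .80. At 53 per group it gives .87, .81 and .77 at the three levels. With only the four times at which Table 2 collects diet and activity, these become .86, .80 and .76.

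**The case against.** The strongest reply is that the quoted sentence is true and sits in the paragraph on the original plan. The revision keeps .025 but does not repeat the .05 claim. A coherent two-test reading also exists: section 8.2 fits two models, for diet and activity, and section 5 calls the primary outcomes behavioral. The and/or list says what the sample will permit, not what will be confirmatory. Main effects were expressly left unpowered. On this view the sections merely need aligning.

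Much of this is fair. The two-model reading can be inferred, and the 27-test figure describes a plan that no section states. The metabolic outcomes would also strain the .05 claim under the original plan, so that part of the problem did not come from the revision.

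The reply does not rescue the claim. Even with two models, the interaction to be tested in each is not chosen, and the first option alone gives four tests. Reading the two analyses as the behavioral and metabolic halves needs error control at .025 within each half, and none is stated. Section 8.2 is the current analysis plan, and it calls the metabolic outcomes part of the primary analysis.

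The caution about power stands: 212 completers requires all 250 to enroll, which is why the lower case appears in step 4. Demoting the clinical outcomes is the sponsor's decision, since it changes primary aim 2.

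**Conclusion.** The concern holds and should be fixed before outcomes are compared by arm. The statement that two tests at .025 give at most .05 is correct. What is missing is a plan with exactly two confirmatory tests, or one with error controlled within each of two parts.

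The nearest multi-test reading, diet and activity with both time interactions, gives an overall error of about .07 to .10. Nine outcomes with one interaction each give .07 to .20. These figures assume every listed test is confirmatory, all nulls are true, tests are two-sided and outcome correlation lies between 0 and .9. They illustrate the exposure and do not estimate the error rate of a settled plan.

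**What to change.** 1. Name exactly two confirmatory tests at .025 each, for example one diet measure and one activity measure on the same single interaction. The sponsor chooses among HC×G, G×time and HC×time. Section 8.1 covers all three under pattern 2, since it sized the smaller of the two time interactions. G×time matches the first goal in section 8.2; HC×G is the nearest remaining two-way test to the second.
2. Delete the three-way expectation from section 8.2 so that it agrees with section 8.1.
3. Label every other interaction, the main effects, and every other outcome in the primary aims or under Table 2's primary headings as secondary, with no claim of overall error control. This includes the metabolic outcomes, smoking, fitness score, Framingham score and diabetes risk score. Align sections 2, 5 and 8.2 and Table 2.
4. If the sponsor prefers to keep more outcomes or interactions primary, delete or restate the .05 claim, or apply a procedure such as Holm and restate power.

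**Cost.** Naming two tests leaves the sample size unchanged. It needs an amendment with IRB approval (section 9.4), and the clinical outcomes lose confirmatory status. If HC×G is chosen, 212 completers reach .80 power under patterns 1 and 2 but not pattern 3 (.78). Keeping four or six behavioral tests under Holm costs the power shown in steps 3 and 4. The documents give no power for the metabolic outcomes, which are measured at fewer times (labs at two; weight, waist and blood pressure at three). Keeping them primary would need a new calculation.

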4. SRA+HC+GRC

Random assignments will be generated using a standard random number generator with uniform distribution to the four groups by the Clinical Genomics Study Unit (CGSU) data manager. The research staff (CRC at site) will use this randomization schema to inform participants of their group assignment.

Follow up visits:

6-week and 3-month – At 6 weeks and 3 months after the baseline visit, participants will be asked to complete selected surveys online (Table 1). The 6 week survey must be completed after the counseling visit and before Health Coaching begins.

6-month – Six months from the baseline visit, participants will return to the clinic to have weight, BP and waist circumference measured (same procedures as baseline visit). Medications will be reviewed and AE's assessed.

Female subjects will be asked if they are currently pregnant and this will be documented.

They will also complete the required surveys as listed, either before their scheduled visit or during their visit at the clinic.

12-month- Twelve months from the baseline visit, participants will return to the clinic for a final visit to have weight, BP and waist circumference measured (same procedures as baseline visit). Medications will be reviewed and AE's assessed.

Lab values from the EMR will be documented for fasting glucose, TC, HDL, LDL, TRIG CRC will check in EMR prior to each subject's 12-month visit. If lab values as stated above are not available from the last 6 months of study participation , then a lipid panel (TC, HDL, LDL, TRIG) and either a FBG or HbA1c will be ordered. Female subjects will be asked if they are currently pregnant and this will be documented.

They will also complete the required surveys as listed, either before their scheduled visit or during their visit at the clinic.

Window of ±one week were allowed for all follow up visits. In order to maximize power and considering

Genetic Risk Testing and Health Coaching for CHD and T2D

Duke IRB# Pro00039569 NCT01884545

recent findings on the stability of metabolic clinical markers absent behavior change, statistical analyses will employ extended inclusion windows for study time-points. Statistical analyses will include: +/-3 weeks for the 6 week survey, +/-7 weeks for the 3 month survey, and +/-11 weeks for the 12 month survey.

Table 1.

STUDY VISITS	GROUP 1	GROUP 2	GROUP 3	GROUP 4

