The second part of the primary analysis will determine the direct and interactive effects of genetic risk information incorporated with standard CHD/T2D risk counseling and a health coaching intervention for CHD/T2D on metabolic outcomes (fasting blood glucose, SBP, BMI, waist circumference, LDL, triglycerides, total cholesterol) over 12 months. The statistical analysis will be the same as above except that the dependent variables will be fasting blood glucose, SBP, BMI, waist circumference, LDL, triglycerides, and total cholesterol.

To address Aim 2, we will examine the mediating effects of level of CHD/T2D genetic risk (number of risk alleles) and consequent reclassification of FRS in the case of CHD risk (decreased, neutral, or increased) on behavior change (diet, physical activity) at 6 months. The goal of this analysis is to quantify the extent to which subgroups of patients exhibit different levels of change in diet and physical activity behavior at 6 months post randomization depending on reclassification of FRS and T2D risk level. We also want to know if the differences depend on whether or not the genetic results were delivered in the context of health coaching. For these analyses, we will use results from only the two groups of patients randomized to receive genetic testing (n=200). Because we will have only two points in time, we will use the simpler linear regression model, with the dependent variable being either diet or physical activity collected at 6 months post randomization. There will be six independent variables: the outcome measured at baseline (a covariate), the results of the genetic testing (entered as two dummy coded variables), a dummy coded variable to indicate the presence or absence of health coaching, and two dummy coded variables representing the interaction of health coaching and the results of genetic testing. We are particularly interested in comparing the diet and physical activity changes of patients whose genetic test results move their Framingham risk or T2D levels either up or down (based on number of higher-risk alleles) to those whose genetic

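### The 176-196 given in 8.1 for coaching-by-genetics applies only to a five-visit model with a within-person correlation of .35 or lower, and its .80-.85 power does not carry over to the metabolic outcomes, least of all the laboratory ones

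*Combined protocol and SAP*

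**What the plan says.** Section 8.1 sets the power problem "in the context of a longitudinal general linear mixed model" with "five levels of time (0, 1.5, 3, 6 and 12 months after randomization", and on error control says: "The type I error rate was set to be no greater than .025 as there will be two primary analyses". Effects are in SD units: "we further assumed that each of the four group means over time would take on standardized mean values". Every row of both revised power tables uses a within-person correlation of .350, with no source, range or sensitivity check. The pattern 2 row for coaching-by-genetics is "2 .025 .80 .350 44 176"; the next row gives 49 per group, 196 in total, for power .85.

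From these rows, item 2 of the closing list in 8.1 says that the reduced trial can still examine this interaction: "comparative effectiveness without time point considered in interaction; estimated sample needed 176-196". Item 1 gives 172-196 for the coaching-by-time and genetics-by-time tests.

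Section 8.2 then extends the primary analysis to metabolic outcomes: "The statistical analysis will be the same as above except that the dependent variables will be fasting blood glucose, SBP, BMI", followed by waist and lipids. Table 2 schedules diet and activity at four time points, weight, waist and blood pressure at three (0, 6, 12 months), and laboratory tests at two (0, 12 months). Section 5.3.1 supports wider analysis windows by reference to "recent findings on the stability of metabolic clinical markers absent behavior change".

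**The concern.** One correlation serves two kinds of test that respond to it in opposite directions. The time interactions are within-person contrasts, so their required number is proportional to 1 - rho, and a low rho is cautious. Coaching-by-genetics without time compares person means between groups. Its required number is proportional to (1 + (k - 1) rho)/k for k visits, so a low rho and a large k are both favourable.

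The figure in item 2 carries no such limit, and no metabolic outcome is measured five times. A null synergy result on glucose, lipids, BMI, waist or SBP would be read as coming from a test with .80-.85 power, when on the outcome's own schedule it may have clearly less.

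**Working it through.** **Inputs.** From 8.1: alpha .025, SD 1, rho .35, five visits, 44 per group for .80, attrition at most 15%. From 5.1: 250 enrolled, so 250 x .85 = 212.5, or 53 per group. From Table 2: visits per outcome. Assumed: compound symmetry and a two-sided 1-df F test with 4n - 4 denominator df (sidedness is not stated).

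**Formula.** The variance of a person's mean over k visits is v = (1 + (k - 1) rho)/k. The interaction contrast d has variance 4v/n, and the noncentrality is d² n/(4v).

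**The plan's own figure.** The pattern 2 cell means are not printed, so 176 cannot be derived from stated inputs alone. Two checks support the model.

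- Back-solving: v = (1 + 4 x .35)/5 = .48. Power .80 at 44 per group implies d = .649. The same d gives .845 at 49 per group, against the stated .85.
- Printed margins: if genetics alone has no effect, the interaction at each time is twice the printed genetics difference. That is 0, .40, .75, 1.15 and .90, with mean 3.20/5 = .64. Power is then .788 at 176 and .834 at 196.

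**Thresholds with d fixed at .649.** Power is .80 when v = .48 x 212/176 = .578, so rho = (k x .578 - 1)/(k - 1):

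- k = 5: .473 (.475 by the exact F test)
- k = 4: .44
- k = 3: .37
- k = 2: .16

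**Power at 53 per group, d fixed at .649**

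| Visits | rho .35 | .5 | .7 | .9 |
|---|---|---|---|---|
| 5 (power model) | .874 | .785 | .674 | .582 |
| 4 (diet, activity) | .850 | .767 | .665 | .579 |
| 3 (BMI, waist, SBP) | .810 | .737 | .649 | .575 |
| 2 (laboratory) | .731 | .680 | .620 | .566 |

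For two visits at rho .35: v = 1.35/2 = .675, and the noncentrality is .649² x 53/(4 x .675) = 8.3, against 9.6 needed for .80.

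**Power at 53 per group from the printed means, genetics alone having no effect**

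| Visits | d | rho .35 | .5 | .7 | .9 |
|---|---|---|---|---|---|
| 3 | (0 + 1.15 + .90)/3 = .683 | .851 | .784 | .699 | .625 |
| 2 | (0 + .90)/2 = .45 | .398 | .359 | .317 | .284 |

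On this version the three-visit threshold is higher. v = .683² x 53/(4 x 9.65) = .64, so rho = (3 x .64 - 1)/2 = .46.

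**The contrast with the time interactions.** Genetics-by-time power at 53 per group rises from .87 at rho .35 to .95 at .50 and .998 at .70.

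**The case against.** Four points can be made on the other side.

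*No correlation is known.* This stands. A reader might infer from the stability remark in 5.3.1 that the plan concedes a high correlation for its metabolic markers, so that power for BMI is known to be poor. The documents do not support that. The remark is qualitative, is conditional on no behaviour change in a trial meant to change behaviour, and concerns visit windows. It lends some support to a higher value and gives no number. The laboratory shortfall does not depend on it, since it appears at .35.

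*The effect was set for behaviour.* Section 8.1 describes the expected synergy in terms of health behaviour, and no metabolic effect size is given. This also stands: every metabolic power figure above borrows a behavioural effect. It is a further reason not to carry .80-.85 over.

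*Baseline adjustment would recover power.* The loss arises partly from averaging a baseline with no effect into the contrast. Adjusting post-baseline means for baseline would gain from a higher correlation; on the five-visit schedule with the printed means, power would be about .99. But 8.2 lists only genetics, coaching and time as independent variables, with time 0 as a level. It uses baseline as a covariate only in the separate 6-month regression. The figures here apply to the plan as written. Partial data from dropouts would add a little power.

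*The trial has a margin.* True for five visits at .35, where 53 per group gives .87. That margin assumes 250 enrolled. The printed minimum of 212 is an enrolment figure that allows for attrition (180/.85 = 212). With 180 completers, 1 + 4 rho = 2.4 x 180/176, and the five-visit threshold is only .36.

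**Conclusion.** The concern holds in a limited form. The 176-196 is consistent with its own assumptions and is not shown to be wrong for a five-visit outcome at a correlation of .35 or lower. It does not transfer unqualified to outcomes with fewer visits or higher correlations.

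A reader might take .47 as one cut-off for all outcomes. It is not: it belongs to five visits, and Table 2 gives no metabolic outcome that many. With three visits, .80 is just reached at .35 and lost above .37 (fixed effect) or .46 (printed means). With two visits it is already missed at .35 on either version.

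These results rest on compound symmetry, 53 completers per group, a pooled effect of .649 SD or the printed means with no effect of genetics alone, and no baseline adjustment. Whether any outcome's correlation exceeds its threshold cannot be settled from the documents.

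**What to change.** In 8.1 item 2:

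- Limit 176-196 to the five-visit model at a within-person correlation of .35 or lower, and do not claim .80-.85 for the metabolic outcomes.
- Add one small table of coaching-by-genetics power on each outcome's own Table 2 schedule, at correlations .35, .5, .7 and .9, labelled as assumptions. The two tables under the working can serve, with the fixed-effect and printed-means versions both shown.
- State that 53 per group comes from 250 x .85 and not from the printed minimum of 212.

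The cost is a few lines and a table. Stated power for the metabolic outcomes becomes less favourable; no patients, visits or analyses are added.
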